4.1 Trial objectives

Primary objective

To investigate whether disease-specific patient education, promotion of a healthy lifestyle and remote PRO-monitoring, delivered through a mobile application based on principles of goal-setting and gamification, can improve self-efficacy in patients with RA. Self-efficacy will be assessed with the Arthritis Self-Efficacy Scale (ASES).

Secondary objectives

- To study if this app-based intervention affects pain catastrophizing (either positively or negatively), assessed with the Pain Catastrophizing Scale (PCS). Pain catastrophizing can be defined as an overly negative cognitive-affective orientation toward pain.

Exploratory objectives

- To study if the intervention's effects on self-efficacy and pain catastrophizing are affected by the interval at which participants are asked to report PROs (the RAID questionnaire either once per week or once per month).
- To study if this app-based intervention leads to changes in physical activity or sleep quality, assessed with the International Physical Activity Questionnaire short form (IPAQ-S) and Pittsburgh Sleep Quality Index (PSQI), respectively.
- To study the feasibility of delivering this intervention through a mobile application, by assessing participants' engagement with the app through the proportion of completed RAID-questionnaires and user-behavior statistics, including the proportion of days with logged activities in the app. No incentives for app-use will be provided, except those needed in the trial as built-in in the app (standard push-messages of the app), in order to provide a representative picture of participants' intrinsic and continued motivation.
- To identify baseline predictors of the intervention's effect on ASES, PCS, IPAQ-S and PSQI scores.
- To describe the evolution over time of scores on the RAID-questionnaire completed in the app, and its association with (changes in) self-efficacy, physical activity, sleep quality, and disease activity assessed at the study visits.

- To describe the evolution of the data that were actively logged by participants relating to their diet, physical activity, stress (such as minutes spent completing relaxation exercises in the application), and sleep, and study their association with disease activity, the RAID, ASES, IPAQ-S, and PSQI.

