6.3 Other investigations

Other than any investigations required as part of routine care, no additional investigations will be carried out for this study.

7. Assessment of efficacy

Efficacy of this app-based educational, monitoring, and lifestyle intervention will be studied by assessing changes in self-efficacy (ASES), physical activity (IPAQ-S) and sleep quality (PSQI), while the intervention's effect on pain catastrophizing will be studied in a non-inferiority setting to exclude any

(negative) effects of systematic PRO-registration on pain perceptions. As stated in the sections on Trial Objectives and Design, the primary endpoint will be the difference in mean change of total ASES-score from baseline to week 16 ± 2 w in the intervention group when compared to the control group, while the intervention's effect on pain catastrophizing was chosen as a secondary endpoint. Sample size calculations were based on obtaining 80% power for both the primary and the secondary endpoint, as outlined in section 9.

In addition to the information obtained from the questionnaires, we will also study participants' continued engagement with the app and its possible effects on intervention efficacy as an exploratory endpoint, as described above.

8. Assessment of Safety

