An additional sample size calculation was conducted for the secondary outcome of change in PCS score from baseline in the intervention group compared to the control group. Based on pooled data from the PCS development/validation studies and a French cohort of patients with RA, the population weighted mean (SD) PCS score is estimated at 20.3 (SD 12.3) (27,35,36). Thus, a clinically important difference in the PCS score, previously proposed as greater than 38% change (27,37), would correspond to a change in total PCS score of greater than 7.7/52. Aiming to exclude any (negative) effect of the intervention on change in the PCS score, we chose a non-inferiority design for this outcome. Given that the effect of the intervention on the PCS score is unknown, we chose the aforementioned minimal clinically important difference of 7.7 as the non-inferiority margin. In other words, non-inferiority will be confirmed if the upper bound of the 95% CI for the intervention's effect on PCS remains within a minimal clinically important margin(38). Following these assumptions and allowing for a 10% dropout rate, a total of 82 participants need to be included (41 in both the control and intervention groups) to demonstrate a non-inferior effect of the intervention on the PCS score with 80% power, a minimal clinically important margin and a two-sided significance level of 0.025. When 120 patients are included as per the primary outcome, and assuming a 10% drop-out rate, we should have 90.2% power to demonstrate non-inferiority for this secondary outcome.

Sample size calculations were conducted via R version 4.2.1, using the packages *pwr* and *epiR* (see Appendix B). In summary, a total of 120 patients will need to be included to assess both the primary outcome and the secondary outcome with at least 80% power, including 60 participants in both the control group and in the intervention group.

As described above, the intervention group will then again be randomized in a 1:1-ratio to assess the exploratory outcomes. The trial will thus not be powered for the exploratory analyses.

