9.2 Analysis

Analyses will be carried out according to the intention-to-treat (ITT) principle, implying that participants will be analyzed based on the group they were originally assigned to.

In this study, the ITT population will consist specifically of all patients in the intervention group who effectively downloaded and installed the Sidekick application at the baseline visit, and all patients assigned to the control group. As stated above, participants in the intervention group will be re-randomized to intervention arm A or B, constituting two additional ITT populations that will only be analyzed exploratorily.

Per protocol (PP) analyses will be carried out as sensitivity analyses, including only those patients who completed the follow-up visit.

The variables described above in sections 4-6 will be extracted from the electronic medical patient file that is employed in all participating centers (KWS). Additionally, user behavior statistics and data actively logged by the patients in the app will be collected and provided for analysis in pseudonymized form by Sidekick Health. The primary and secondary outcome data of this study will be collected via questionnaires on the MyNexuzHealth app, or if not possible in pen-and-paper format at the outpatient clinic. All study-related information will be assembled and prepared for further analysis in an electronic CRF developed in REDCap. P-values <0.05 will be considered as statistically significant for all analyses. Missing data will be handled with multiple imputation by chained equations when data can be assumed to be missing at random. Descriptive statistics for baseline participant characteristics will be provided as means (\pm SD), medians (IQR) or proportions depending on data distribution.

Primary endpoint

The difference in mean change of total ASES (Arthritis Self-Efficacy Scale) score from baseline to week 16 \pm 2w in the intervention group when compared to the control group will be evaluated with an unpaired t-test or Wilcoxon rank sum test depending on distribution of the ASES-score. As a sensitivity analysis, we will additionally assess the difference between groups in week 16 scores using ANOVA adjusted for the baseline score. Furthermore, differences in the pain and other symptoms subscales of the ASES will be presented separately.

Secondary endpoints

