- The difference in mean change of total PCS score from baseline to week 16 \pm 2w in the intervention group will be compared to that in the control group, using an unpaired t-test or Wilcoxon rank sum test depending on distribution of the PCS score. As a sensitivity analysis, we will additionally assess the difference between groups in week 16 scores using ANOVA adjusted for the baseline score.

Exploratory endpoints

- The difference in mean change of total ASES score from baseline to week 16 \pm 2w in the intervention arm with weekly RAID questionnaires will be compared to that in the intervention arm with monthly RAID questionnaires, using an unpaired t-test or Wilcoxon rank sum test depending on distribution of the ASES-score. As a sensitivity analysis, we will additionally assess the difference between groups in week 16 scores using ANOVA adjusted for the baseline score.

- The difference in mean change of total PCS score from baseline to week 16 \pm 2w in the intervention arm with weekly RAID questionnaires will be compared to that in the intervention arm with monthly RAID questionnaires, using an unpaired t-test or Wilcoxon rank sum test depending on distribution of

the PCS score. As a sensitivity analysis, we will additionally assess the difference between groups in week 16 scores using ANOVA adjusted for the baseline score.

- The difference in mean change of total IPAQ-S score from baseline to week 16 ± 2w in the intervention group when compared to the control group will be evaluated with an unpaired t-test or Wilcoxon rank sum test depending on distribution of the IPAQ-S score. As a sensitivity analysis, we will additionally assess the difference between groups in week 16 scores using ANOVA adjusted for the baseline score.
- The difference in mean change of total PSQI score from baseline to 16 ± 2w in the intervention group when compared to the control group will be evaluated with an unpaired t-test or Wilcoxon rank sum test depending on distribution of the PSQI score. As a sensitivity analysis, we will additionally assess the difference between groups in week 16 scores using ANOVA adjusted for the baseline score.

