# Accounting for possible need for non-parametric tests
samplesize <- round(samplesize*1.15)

#---- Secondary outcome: PCS (non-inferiority)
power <- epi.ssninf(treat = 20.3, control = 20.3, sd = 12.3, delta = 7.7, n = NA, r = 1,
power = 0.80, alpha = 0.025)

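### Section 9.2 does not carry out the non-inferiority analysis that sections 7 and 9.1 and Appendix B set for the Pain Catastrophizing Scale (PCS)

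*Combined protocol and SAP*

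**What the plan says.** **Design.** Section 7 states that "pain catastrophizing will be studied in a non-inferiority setting to exclude any" negative effects on pain perception. Section 9.1 agrees: "we chose a non-inferiority design for this outcome". It sets the margin, "we chose the aforementioned minimal clinically important difference of 7.7 as the non-inferiority margin", and a decision rule: "non-inferiority will be confirmed if the upper bound of the 95% CI" for the effect on PCS stays within that margin. The sample-size code in Appendix B uses "power = 0.80, alpha = 0.025". The text of 9.1 calls this 0.025 level two-sided.

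**Objective.** Section 4.1 puts the question in both directions: "To study if this app-based intervention affects pain catastrophizing (either positively or negatively". It names no test, null value or significance level.

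**Analysis.** The PCS bullet in section 9.2 says that the mean change "in the intervention group will be compared to that in the control group, using an unpaired t-test or Wilcoxon rank sum test", depending on distribution. This is in substance the wording used for the superiority endpoint, the Arthritis Self-Efficacy Scale (ASES). The sensitivity analysis is a baseline-adjusted comparison of week 16 scores. Neither mentions a margin, a confidence interval, a null value or sidedness, and neither refers back to 9.1. The same section adds, without exception: "P-values <0.05 will be considered as statistically significant for all analyses".

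**The concern.** An unpaired t-test with p<0.05 is by default a test of zero difference, and a rank-sum test gives a p-value with no interval for the mean difference to set against 7.7. Neither tests the hypothesis in 9.1, that a worsening of 7.7 points or more can be excluded. An analyst working from 9.2 alone would obtain a p-value against zero and could report a non-significant result as reassurance. A non-inferiority design exists to prevent that inference.

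The level differs too. The 95% CI rule corresponds to one-sided 0.025, while 9.2 gives 0.05 for everything.

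This matters because PCS is the trial's formal check for harm. Section 3 names increased catastrophizing as a possible negative effect of such apps, and section 8.2 states that adverse event recording does not apply. The trial is also open-label, so the rule is best settled in the analysis section before data are examined.

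**Working it through.** **Inputs.** From section 9.1 and Appendix B: SD 12.3, margin 7.7, true difference 0, 1:1 allocation, alpha 0.025, and 120 randomized less 10% dropout = 108 analysed, so 54 per group. Differences are intervention minus control in mean change; positive means worse.

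**1. Reproduce the plan's figure.**
- SE = 12.3 × √(2/54) = 2.367.
- Power at one-sided 0.025 = Φ(7.7/2.367 − 1.96) = Φ(1.293) = 0.902. This matches the stated 90.2%.
- One-sided 0.05 would give 94.6%. A literal two-sided 0.025 (one-sided 0.0125) would give 84.4%.
- At one-sided 0.025 and 80% power, n per group = 2 × [12.3 × (1.96 + 0.842)/7.7]² = 40.06, rounded up to 41, or 82 in total before any dropout allowance.

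So the level actually used is one-sided 0.025, in agreement with the 95% CI rule. Only the two-sided label in 9.1 is out of line.

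**2. Cut-offs on the observed difference, if the observed SD is 12.3.**
- t(0.975, 106 df) = 1.983, so the 95% CI half-width is 1.983 × 2.367 = 4.69.
- Rule in 9.1: non-inferior if the difference is below 7.7 − 4.69 = 3.01.
- Default reading of 9.2 (two-sided t-test of zero at 0.05): significant worsening if the difference exceeds 4.69.
- Blanket 0.05 applied to a one-sided non-inferiority p-value: t(0.95, 106 df) = 1.659, so the cut is 7.7 − 1.659 × 2.367 = 3.77.

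**3. How often an estimate falls between 3.01 and 4.69** (non-significant against zero, non-inferiority not shown), taking the estimate as normal with SE 2.367:

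| True worsening | Calculation | Probability |
|---|---|---|
| 0 | Φ(1.983) − Φ(1.270) | 0.078 |
| 2 | Φ(1.138) − Φ(0.425) | 0.208 |

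With 1.96 in place of 1.983 the figures are 0.073 and 0.195.

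**4. False non-inferiority rate at a true worsening of 7.7.** By construction it is 2.5% under the 95% CI rule and 5% if one-sided 0.05 is used.

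**5. Example.** Observed worsening 3.5 points:
- 95% CI 3.5 ± 4.69 = −1.19 to 8.19. It crosses 7.7, so non-inferiority is not shown under 9.1.
- Test of zero: t = 3.5/2.367 = 1.48, p = 0.14.
- One-sided non-inferiority test: t = (7.7 − 3.5)/2.367 = 1.77, p = 0.039. That passes at 0.05 and fails at 0.025.

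**6. Dependence on the SD.** The plan applies a cross-sectional SD to change scores. The two cuts coincide when the half-width is 7.7/2 = 3.85, that is at SD 3.85/(1.983 × √(2/54)) ≈ 10.1. Below that SD of change, a result can be significantly worse than zero and still non-inferior. At SD 8 this covers differences of 3.05 to 4.65.

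**The case against.** The strongest reply is that the rule already exists. Section 9.1 states prospectively how non-inferiority will be confirmed, and section 7, outside the sample-size section, repeats the design. Nothing gives 9.2 precedence over them, and an unpaired t-test yields the CI that 9.1 needs. In the t-test branch the sections can therefore be read together. This stands, and it limits the fault to an omission and a mismatch. It does not remove the blanket 0.05 threshold, nor does it help the rank-sum branch.

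Two stronger readings are tempting but unsupported. A reader might infer that the plan specifies two rival tests. It does not: 4.1 words a question without naming a test, 9.2 states neither a zero null nor sidedness, and 9.1 never uses the term one-sided, which is inferred from the CI rule and the reproduced power.

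A reader might also infer that one result would receive two contradictory verdicts. Between 3.01 and 4.69, no significant difference and non-inferiority not shown are both true; the result is inconclusive. Significantly worse yet non-inferior is likewise a coherent outcome. No section says that p≥0.05 will be read as no effect. The probabilities above show how often the two statements part company; they are not error rates of the plan.

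The doubling to 5% is also conditional: it needs someone to compute a one-sided non-inferiority p-value and judge it at 0.05, whereas the only stated non-inferiority rule is a CI bound.

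**Conclusion.** The concern holds as an omission with a conflicting threshold. Read literally, 9.2 delivers a p-value against zero, a rank-sum p-value with no interval to compare with 7.7, or, if its 0.05 is applied to a one-sided non-inferiority p-value, a test with twice the intended error. None of these is the analysis that 9.1 powered at 90.2%.

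The sizes rest on SD 12.3 for change and 54 analysed per group. The cut-offs would shift with the observed SD, but the need to state the rule in 9.2 would not. This should be corrected before analysis; it does not affect the sample size of 120.

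**What to change.** Rewrite the PCS bullet in section 9.2:

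- **Main analysis:** the two-sided 95% CI for the intervention-minus-control difference in mean change. Non-inferiority is declared if the upper bound is below 7.7 (one-sided 0.025).
- **Two-directional objective:** use the same interval. Claim improvement if the upper bound is below 0. Report worsening if the lower bound is above 0, whether or not non-inferiority holds. An upper bound below 0 is necessarily below 7.7, so no alpha split is needed.
- **Threshold:** exempt this analysis from the p<0.05 line, and state that a non-significant difference from zero is not evidence of non-inferiority.
- **Non-normal data:** name in advance how the interval for the mean difference will be obtained, and keep any rank-sum p-value as supportive only.

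In section 9.1, and where the synopsis repeats it, relabel the 0.025 level as one-sided.

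The cost is wording only: no extra patients, data or alpha.

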4.3 Secondary endpoints

Difference in mean change of total PCS (Pain Catastrophizing Scale) score from baseline to week 16 ± 2w in the intervention group when compared to the control group. The PCS is a patient-reported questionnaire with 13 items scored on a 0-4 Likert scale, resulting in a total score of 0-52 with sub scores for rumination, magnification, and helplessness. Higher scores indicate more catastrophic perceptions concerning pain.

4.3b Exploratory endpoints

- Difference in mean change of total ASES score from baseline to week 16 ± 2w in the intervention arm with weekly RAID questionnaires when compared to the intervention arm with monthly RAID questionnaires.
- Difference in mean change of total PCS score from baseline to week 16 ± 2w in the intervention arm with weekly RAID questionnaires when compared to the intervention arm with monthly RAID questionnaires.
- Difference in mean change of total IPAQ-S score from baseline to week 16 ± 2w in the intervention group when compared to the control group. The IPAQ short form is a 7-item questionnaire enquiring about physical activities during the last 7 days. A specific activity score is obtained for different domains, each being multiplied with the accompanying mean metabolic equivalent (MET) value. This leads to a total score corresponding with low, moderate, or high physical activity.
- Difference in mean change of total PSQI score from baseline to week 16 ± 2w in the intervention group when compared to the control group. The PSQI is a patient-reported questionnaire developed to measure sleep quality through 19 items across 7 domains. The resulting total score ranges from 0-21, with scores of 5 or higher being defined as poor sleep quality.
- To describe participants' continued engagement with the app and to compare it between the weekly and monthly PRO subgroups. Engagement will be defined as:
 - * The proportion of RAID questionnaires with at least one completed item in the Sidekick app, compared to the total number of RAID questionnaires prompted by the app for each participant

during the study period.

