* User-behavior statistics: Sidekick Health will provide pseudonymized logged data from the app. This includes “passive” usage information such as the number of times participants logged into the app or the number of goals that were set, as well as data that were actively logged by participants relating to their physical activity, diet, stress (such as minutes spent completing relaxation exercises in the application), and sleep.

- Baseline predictors of the intervention’s effect on ASES, PCS, IPAQ-S and PSQI scores: candidate predictors include demographic characteristics, disease-related characteristics (autoantibody status, current and previous therapy, disease duration, ...), and measures of participant engagement (as previously defined).

- The evolution and fluctuation over time of scores on the RAID-questionnaire completed in the app, and its association with self-efficacy, physical activity, sleep quality, and disease activity assessed at the study visit. The RAID is a patient-reported questionnaire with 7 items scored on a 0-10 numeric rating scale, enquiring about the impact of RA on different aspects of physical and mental health. Disease activity will be assessed as in usual care, with composite scores such as the DAS28-CRP and SDAI (both are composed of the number of tender joints and swollen joints, patient’s global assessment of disease activity on a visual analogue scale VAS, and C-reactive protein CRP; the SDAI additionally includes the physician’s global assessment of disease activity).

- The association of data actively logged in the app (step counts, exercise activities, diet, sleep quality, stress level, and energy level) with the validated outcome measures RAID, IPAQ-S, PSQI, ASES, and DAS28-CRP.

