- Pain catastrophizing: The PCS is a patient-reported questionnaire with 13 items scored on a 0-4 Likert scale, resulting in a total score of 0-52 with subscores for rumination, magnification, and helplessness (27). Higher scores indicate more catastrophic perceptions concerning pain.
- Physical activity: The IPAQ short form is a 7-item questionnaire enquiring about physical activities during the last 7 days (28). A specific activity score is obtained for different domains, each being multiplied with the accompanying mean metabolic equivalent (MET) value. This leads to a total score corresponding with low, moderate or high physical activity.
- Sleep quality: The PSQI is a patient-reported questionnaire developed to measure sleep quality through 19 items across 7 domains (29). The resulting total score ranges from 0-21, with scores of 5 or higher being defined as poor sleep quality.

- Disease activity will be monitored in both participant groups with the DAS28-CRP and SDAI scores, using internationally validated cut-offs. DAS28-CRP is a composite score that combines a patient's global assessment of disease activity, a clinical examination with counts of painful and swollen joints, and CRP as an inflammatory laboratory parameter (30). SDAI is an analogous composite score that additionally includes the physician's/evaluator's global assessment of disease activity and has its own validated cut-offs (31). These examinations are part of routine care.

- Results of both clinical data and the obtained questionnaires will be extracted from the electronic medical patient file used in UZ Leuven and other participating centers (KWS) or, if not possible, from the completed pen-and-paper forms.

Intervention phase (between baseline and week 16 ± 2w visit)

While using the SideKick Health app, patients in the intervention group will have the opportunity to actively log data relating to their diet, physical activity, sleep quality, stress (such as minutes spent completing relaxation exercises in the application), vital signs, and fill out short questionnaires, for example the RAID questionnaire, integrated in the application. Among these, only completion of the RAID questionnaire is actively stimulated and expected as part of the study, all other functions can be used on a voluntary basis.

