- Participant engagement with the app will be analyzed descriptively as 1) the proportion of RAID questionnaires with at least one completed item in the Sidekick app, compared to the total number of RAID questionnaires prompted by the app for each participant during the study period; and 2) several user behavior statistics as described elsewhere. Additionally, participant engagement will be compared between the weekly and monthly RAID groups with unpaired t-tests or Mann-Whitney-U tests depending on data distribution.
- Candidate predictors of a favorable effect of using the Sidekick app on self-efficacy, sleep and physical activity will be studied exploratively with (multiple) linear regression.
- The evolution over time of the RAID scores at baseline, provided in the app (intervention group only) and at week 16 ± 2w, and their association with other outcomes including ASES, IPAQ-S, PSQI and DAS28-CRP/SDAI scores, will be described with linear mixed effects regression models.
- The association of data actively logged in the app (step counts, exercise activities, sleep quality, stress level, and energy level) with (changes in) the validated outcome measures RAID, IPAQ-S, PSQI, ASES, and DAS28-CRP/SDAI collected at baseline and week 16 ± 2w will be reported as Spearman or Pearson correlation coefficients depending on data distribution.

10. Quality assurance

Data collection tools and source document identification:

Source data will be collected and recorded in the study participants' files/medical records. They will be kept on a secured location at all times. The collection and processing of source data (from subjects enrolled in this study) will be limited to those data that are necessary to fulfill the objectives

of the study. These data must be collected and processed with adequate precautions to ensure confidentiality and compliance with applicable data privacy protection laws and regulations. Appropriate technical and organizational measures to protect the data against unauthorized disclosures or access, accidental or unlawful destruction, or accidental loss or alteration must be put in place. Personnel whose responsibilities require access to personal data agree to keep the data confidential.

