The Terms and Conditions in the informed consent form (ICF) also apply to the storage and handling of personal data, specifically account registration information, user-logged data and user behavior data.

According to these general Terms and Conditions, account registration information, data logged by users in the SidekickHealth application, and user behavior data are stored in the Google Cloud SQL service on behalf of GoodlifeMe, the SidekickHealth manufacturer. Google does not have access to this information for any other reason than to store it. Account registration information includes a user's name, email and chosen password, as well as information about their height, weight, age,

gender and profile picture if app users choose to supply this. To protect the personal email address of the user, we will label the individual patient account with a unique code (coded study email address) that will also serve as the study identification code for that individual in the eCRF. This code will be matched with the unique patient identification number in the KWS (EAD number) and kept in a separate file only available to the local study team. Logged data includes only the information actively logged by the user relating to their diet, physical activity, stress (such as minutes spent completing relaxation exercises in the application), vital signs, and questionnaires entered into the application. User behavior data include specific information about how participants use the application, such as how often the app is used, to what extent the educational modules have been accessed, how often certain lifestyle information is uploaded, to what extent patients have used a wearable together with the app etc... Upon deletion of the Sidekick account, or when the user has not logged any activity in the application for a period of two years, all personally identifiable data is deleted from the Google Cloud SQL service.

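### The weekly-versus-monthly engagement comparison includes login counts, and possibly logged days, that can favour the weekly arm through the RAID schedule alone

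*Combined protocol and SAP*

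**What the plan says.** Section 4.3b sets the exploratory endpoint: "To describe participants' continued engagement with the app and to compare it between the weekly and monthly PRO subgroups". Engagement then has two components.

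- **RAID completion.** "The proportion of RAID questionnaires with at least one completed item in the Sidekick app", which section 9.2 sets against a denominator specific to the person: "compared to the total number of RAID questionnaires prompted by the app for each participant".
- **User-behaviour statistics.** These include "usage information such as the number of times participants logged into the app", the number of goals set, and data logged on physical activity, diet, stress and sleep. The exploratory objective in section 4.1 adds a further measure, "including the proportion of days with logged activities in the app", which is not repeated in 4.3b or 9.2.

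Section 9.2 first describes both components and then says that "participant engagement will be compared between the weekly and monthly RAID groups with unpaired t-tests or Mann-Whitney-U tests". It does not limit the test to the first component, and it applies a 0.05 significance threshold to all analyses.

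Section 4.4 assigns arm A one in-app RAID per week and arm B one per month, with 30 participants in each. Section 6.1 says that, among the app's functions, "only completion of the RAID questionnaire is actively stimulated and expected as part of the study"; everything else is voluntary.

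On whether a RAID is logged data, the sections differ. Section 13 (Data Handling) lists "vital signs, and questionnaires entered into the application" among the logged data. Section 4.3b and the flowchart in 4.6 list logged data without the RAID.

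**The concern.** A participant has to open the app to complete an in-app RAID. A raw login count therefore contains the number of RAIDs the participant was asked for, and that number is what was randomised. Two arms with the same voluntary use can differ on logins because one was asked to open the app about four times as often. The same applies to active days if a RAID-only day counts. No section sets RAID-driven sessions aside.

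The stake is interpretation. Section 4.1 presents engagement as the feasibility measure and wants it to reflect intrinsic, continued motivation. A significant excess of logins in arm A could be reported as weekly reporting raising engagement when it partly or wholly restates the allocation. Section 4.3b also lists engagement measures as candidate predictors of the intervention's effect, and section 7 plans to relate engagement to efficacy, so a schedule-driven component could carry over there.

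**Working it through.** The plan gives no effect size, power or expected value for this comparison, so there is no figure to reproduce.

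**Inputs from the protocol.** Follow-up of 16 weeks with a 2-week window either side (112 days, range 98 to 126); RAID weekly versus monthly; 30 per arm; dropout of at most 10%, hence 30 × 0.9 = 27 per arm.

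**Assumptions.** About 4 monthly prompts (3 to 5 tried); adherence, voluntary use and overlap varied as below.

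**Step 1: ceiling from the schedule alone** (full adherence, no overlap with other use).

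- Sessions: 16 − 4 = 12.
- Days: 16/112 = 14.3% versus 4/112 = 3.6%, a gap of 10.7 percentage points.
- Across the visit window and 3 to 5 monthly prompts: from (14 − 5)/98 = 9.2 to (18 − 3)/126 = 11.9 points.
- At 50% adherence in both arms: 8/112 = 7.1% versus 2/112 = 1.8%, and 8 − 2 = 6 sessions.

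**Step 2: overlap.** For logins, let a and b be adherence in arms A and B, and s the share of RAIDs answered in a session that would have been opened anyway. The gap is (16a − 4b)(1 − s). At full adherence that is 12 for s = 0, 6 for s = 0.5 and 0 for s = 1.

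For days, if a RAID counts as logged and falls on a random day, and v is the mean share of days with voluntary use, the expected gap is (16a − 4b)(1 − v).

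**Step 3: false significance for active days.** A simulation gave both arms the same voluntary use: 27 per arm, 1,000 runs per setting, each person's share of voluntary days drawn from a Beta distribution with concentration 2. RAIDs counted as logged and fell on random days.

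| v | Adherence A/B | Expected gap (days) | Simulated gap | Mann-Whitney p<0.05 | t-test p<0.05 |
|---|---|---|---|---|---|
| 10% | 100/100% | 12 × 0.9 = 10.8 | 10.79 | 97% | 59% |
| 10% | 70/70% | 8.4 × 0.9 = 7.6 | 7.34 | 92% | 33% |
| 10% | 50/80% | 4.8 × 0.9 = 4.3 | 4.14 | 74% | 15% |
| 30% | 100/100% | 12 × 0.7 = 8.4 | 8.62 | 33% | 22% |
| 30% | 70/70% | 8.4 × 0.7 = 5.9 | 6.07 | 19% | 12% |
| 30% | 50/80% | 4.8 × 0.7 = 3.4 | 3.13 | 9% | 7% |
| 50% | 100/100% | 12 × 0.5 = 6.0 | 6.07 | 10% | 11% |
| 50% | 70/70% | 8.4 × 0.5 = 4.2 | 3.82 | 8% | 7% |
| 50% | 50/80% | 4.8 × 0.5 = 2.4 | 2.68 | 6% | 6% |

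If half of the RAIDs that would fall on a no-use day are moved to a day of voluntary use, the Mann-Whitney rates at v = 10% become 81%, 68% and 40%. If all are moved, the gap disappears and rejection is about 3–7%. Leaving out RAID-only days also gives about 3–7% in every setting. The rates depend on the assumed Beta shape, which at v = 10% puts many participants close to no voluntary use.

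**Step 4: the RAID-completion proportion.** Its denominator is the participant's own prompts, so equal adherence gives equal proportions. In the 50/80% rows it shows the weekly arm as less engaged, while the day count on the same data shows it as more engaged.

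**The case against.** The other side has good arguments. Engagement is analysed mainly descriptively, the comparison is exploratory, and section 9.1 says the trial is not powered for it. Any reader knows that one arm was prompted weekly. Remote PRO monitoring is part of the intervention, so RAID sessions are a legitimate form of use, and total use per arm is a valid quantity if labelled as such. All of this stands. It limits the severity and supports keeping RAID-inclusive counts as description. It does not justify testing an unscaled count between arms whose counts differ by design.

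Three stronger readings are tempting, and the documents do not support them.

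- **That logged days do include RAID entries.** Only section 13 points that way, in a description of what the app manufacturer stores. Sections 4.1, 4.3b and 4.6 name the RAID apart from logged data. The text is ambiguous, and if RAIDs are excluded the 14.3% versus 3.6% gap does not arise. The login problem does not depend on this.
- **That the weekly arm would look more engaged purely because of its schedule.** The RAID-completion proportion and the number of goals set are not mechanically inflated, and more frequent prompting may truly raise voluntary use.
- **That RAID completion is itself biased because the arms are sampled at different times.** Both arms are followed for the same 16 ± 2 weeks, and the monthly prompt dates are not given. If completion fell linearly from 90% to 50% over weeks 1 to 16, weekly prompts (mean week 8.5) would average 70%. Monthly prompts at weeks 4, 8, 12 and 16 would average 66%, and at weeks 1, 5, 9 and 13 they would average 74%. The direction is unknown.

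**Conclusion.** The point holds for login counts, and for days with logged activities only if RAID entries count as logged data. As written, the plan allows a between-arm test on measures into which the randomised schedule is built.

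The figures of 12 sessions and 10.7 percentage points of days are a ceiling for 112 days, 16 versus 4 RAIDs, full adherence and no overlap. Under the assumptions tried, the chance of a falsely significant difference in active days ranges from near certain (97%, Mann-Whitney, low voluntary use) to about nominal (heavy voluntary use, or RAIDs done on days of voluntary use). The protocol gives no figure that would place the trial within that range.

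The proportion of prompted RAIDs completed is unaffected, and the primary and secondary endpoints are not touched. Severity is low.

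**What to change.** In sections 4.3b and 9.2:

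1. State that RAID entries do not count as logged activity for the weekly-versus-monthly comparison. This also settles the difference with section 13.
2. Base that comparison on non-RAID use, excluding sessions or days whose only entry is a RAID, alongside the existing proportion of prompted RAIDs completed. Keep that proportion over all prompts: it is already normalised, and limiting it to shared prompts would discard about 12 of 16 weekly ones.
3. Report RAID-inclusive logins and active days descriptively for each arm.

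Non-RAID activity that follows a RAID prompt still counts, so a genuine effect of weekly prompting on voluntary use is preserved.

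The cost is a few sentences and a filter on the app export, with no new data and no burden on participants. There is one small downside: if the export does not record what was done in a session, login counts stay descriptive and active days with non-RAID entries carry the comparison.
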